**Study Protocol & Statistical Analysis Plan**

**NCT Number: NCT05080426**

**June 10, 2024**

## **Written Description of the Clinical Study (including objectives, design, and methods)**

**Key Objectives:** Our key technology objectives are: 1) develop intervention implementation support products to enhance usability and adoption; 2) develop an eLearning management system to enhance user engagement and delivery processes including automation of feedback reports to motivate behavior change and enhance change sustainability; 3) develop a new Supervisor Support for Family Care and Sick Leave Use Module augmenting the core FSST program (designed to increase overall family supportive supervisor behaviors) to also increase targeted support for the use of family care and personal sick time leaves, which many workers face difficulties accessing without fear of job penalties; 4) test and evaluate FSST 2.0 for commercialization readiness.

### **Design & Methods:**

#### **Organizational Settings**

Data were collected via surveys of managers and their direct reports from two universities in the U.S.: a medical university located in the Southwest region (referred to as university 1) and a public university located in the Midwest region (university 2). University 1 focuses on cancer treatment, conducts clinical trials, and trains students in their School of Health Professions. In total, approximately 5,000 trainees participate in university 1 educational programs each year, including clinical residents and fellows, nursing trainees, research trainees, student program participants, and interns. This organization employs approximately 22,000 individuals, including over 1,700 faculty members. University 2 is a unionized, public institution with over 15,000 students that employs over 500 faculty and 1,000 staff members.

Data were collected from both managers (defined as anyone in a supervisory role in a formal capacity – i.e., someone with direct reports) and their direct reports (referred to as employees) over the course of approximately 5 months (see Figure 1 for a timeline of research). For both universities, participants completed a baseline survey and two follow-up surveys approximately 3 and 5 months after the baseline survey (referred to as Times 1, 2, and 3).

#### **Participants, Recruitment, and Survey Procedures**

An overview of the timeline of the study can be seen in Figure 2. Each organization designated a primary point of contact for the research team. This individual developed a list of all managers and employees who would be invited to participate in the study and helped facilitate recruitment. Each point of contact provided invitees' names, work email addresses, role designations (i.e., manager or employee), and identified each invitee's manager to allow for linking in subsequent data analyses. These details were uploaded into a customized online learning management system (LMS), which is a software application that has the capability to automate the delivery and tracking of educational programs, such as the training in the current study. This LMS system sent out recruitment emails to managers and employees that provided participants a link to complete online surveys and (for managers) participate in training activities.

The contact at university 1 randomly selected 368 managers from the total pool of managers who completed one or more of the organization's leadership development programs, which are designed to teach foundational leadership skills and behaviors. For those managers with 12 or fewer direct reports, all direct reports were invited to participate in the study. For all other managers (i.e., those with 12+ direct reports), 12 direct reports were randomly chosen and

invited to participate. This resulted in a total of 1,899 employees being invited to participate at university 1. The contact at university 2 provided a list of names and emails for all academic managers at the university and their direct reports (136 managers and 811 employees). Non-academic managers were excluded from the study per the university's determination.

At both universities, a leader at the organization (i.e., the Associate Vice President of the Leadership Institute at university 1 and the Provost at university 2) sent an email to all potential participants one week prior to data collection describing the purpose of the study and notifying participants to expect recruitment emails from the research team via the LMS system. Potential participants were sent four recruitment emails for the Time 1 survey over the course of approximately one month.

After Time 1 recruitment, the intervention training became available for managers at university 1 (described below). These managers were sent five recruitment emails about the training over the course of approximately one month. Additional reminders about behavior tracking were sent to those managers who had completed both training modules shortly after the training closed. After the training closed, all managers invited to participate in the baseline survey at university 1 were sent an email by the Leadership Institute inviting them to participate in a webinar, approximately one month after the training closed.

Following the webinar, managers and employees at both universities were invited to participate in Time 2 and Time 3 surveys, which fell approximately 3 and 5 months after Time 1 survey. Prior to each survey, the same leader who had previously announced the study at each university emailed all invitees to announce the follow-up surveys and share that invitations from [masked company name] would follow. Participants received three reminders about the Time 2 survey and four reminders about the Time 3 survey. Managers at university 2 (the control group) were offered the intervention at the conclusion of the study.

The intervention included multiple components for managers: two online training modules (created by [company name masked for review]), a 10-day online behavior tracking exercise, and an online webinar. The online training and behavior tracking components were implemented through an LMS created by [company name masked for review], in coordination with [company name masked for review].

The first online training module was developed by [masked company name] in coordination with [masked company name], based on previously studied interventions (e.g., Kossek, Hammer, Kelly, & Moen, 2014). The module, titled *Supportive Supervision and Management for Family and Personal Life*, focused on work-life and family-supportive supervisor behaviors more broadly, including examples of work-life conflict and its implications, the importance of family-supportive supervisor behaviors for employees and organizations, and types of family and personal support, including emotional support, job and personal problem-solving support, creative work-family management, and role modeling. The content also covered performance support behaviors, including measurement and direction, feedback and coaching, providing resources, and support for change. Similar content and interventions have been found in previous research to benefit employees' safety and other behaviors at work (e.g., Hammer et al., 2016), as well as outcomes like job performance, organizational commitment, engagement, job satisfaction, and turnover intentions (Odle-Dusseau, Hammer, Crain, & Bodner, 2016).

[figure not shown]
The second online training module was developed by [masked company name] and the eLearning instructional designers at the [masked company name] utilizing content unique to this study. Titled *Leaders and Leaves: Supporting Employee Use of Paid Family and Sick Leave*

*Policies*, this module focused on increasing supervisor support for paid family care and sick leave use. More specifically, this training focused on developing work-life leadership skills by helping managers learn to increase employees' awareness of the availability of paid family and sick leave policies and introducing other behaviors managers could enact to support use of paid family and sick leave policies with the ultimate goal of increasing the effectiveness of existing paid family and sick leave policies. Behaviors focused on listening and emotional support, education and policy access, reassurance and minimization of negative perceptions, organizing work to support leaves in ways that benefit both the organization and the employee, enhancing employee experiences of leave, and role modeling.

[figure not shown]
Each module took approximately 30 minutes to complete, included both active listening and participation components (e.g., matching activities; quizzes), and provided multiple examples of situations managers may encounter in their work, coupled with examples of supportive strategies to utilize in each situation. After completion of the online training, managers were asked to track the number of supportive behaviors they engaged in across 10 work days as a way to practice and implement the materials discussed in the online training. Managers were asked to set goals in the LMS for the number of family and personal support behaviors, performance support behaviors, and leave use support behaviors they would enact over the 10-day period. Managers were encouraged to set goals that totaled one to two times the number of direct reports they supervised (e.g., if a manager supervised 10 employees, they were encouraged to set goals of 10-20 instances of support behavior over the 10 work days they selected for tracking). Managers received reminders on each of the 10 days they selected for tracking; reminders included links to the behavior tracking section of the LMS to provide an opportunity to easily track the number of behaviors enacted each day.

Finally, managers were invited via email to attend one of two virtual webinars led by the co-founders of [masked company name]. The webinars contained the same content but were offered on different dates and times for participant convenience. All managers were invited to participate, regardless of whether they completed the online training. Each virtual, one-hour webinar reiterated the main points from the online training and allowed for a discussion among managers related to course content, including sharing their own insights/personal experiences and asking questions about course materials. See Figure 1 for participation numbers for the intervention components. At university 1 (i.e., the intervention organization), a total of 174 (47% of recruited managers) completed at least one component of the training.

**Figure 1.** Timeline of research design and data collection at intervention and control sites.

**Figure 2.** Timeline of research design and data collection at intervention and control sites.

**Data Analysis:** The scores of embedded quizzes will be analyzed using paired t-tests to test the improvement in the supervisors' learning. The pre- and post-training Workplace Assessment data will be coded and entered using IBM® SPSS ® Statistics software for analysis. Descriptive statistics (means, frequency counts) will be used to ensure that the data are within pre-specified valid ranges defined for each variable. Internal consistency reliability analyses will be conducted on all Likert-type measures. Descriptive statistics (means, frequency counts, percentages) will be used to describe the sample, and the aggregated means of family-supportive supervisor behaviors and employee outcome variables. The data will be generated from a clustered-design with all participating employees within participating supervisors and employers at two time-points. Given the clustered nature of the data, standard general linear and generalized linear mixed model approaches for clustered designs (i.e., hierarchical linear models, multilevel models; Murray, 1998; Murray, Varnell, & Blitstein, 2004) will be used for the analyses to detect changes between pre- and post-training, and to detect group differences (e.g., Condition A vs. Condition B; employees with vs. without eldercare responsibilities) in the relationships between supervisors' family-supportive behaviors and employee outcomes. Focus group transcripts will be entered into ATLAS.ti, a qualitative software program for data analysis. ATLAS.ti is a powerful tool for analyzing textual data. Using the coding functions of the program, we will analyze the transcripts to identify common themes around the perceived usefulness of the program using open coding procedures. We will then assess the associations among these themes and categories using axial coding procedures (Stauss & Corbin, 1998).

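### Condition coincides with employer and manager sampling frame, yet the Data Analysis section defines no between-arm contrast in change from Time 1 and no limit on the conclusion

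*Combined protocol and SAP*

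**What the plan says.** Participants, Recruitment, and Survey Procedures describes two different ways of choosing managers.

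- **University 1.** The contact "randomly selected 368 managers from the total pool of managers who completed one or more of the" organisation's leadership development programmes, which are "designed to teach foundational leadership skills and behaviors". With at most 12 direct reports invited per manager, this gave 1,899 employees.
- **University 2.** The contact "provided a list of names and emails for all academic managers at the university and their direct reports (136 managers and 811 employees"). The list was restricted by role, at that university's own decision: "Non-academic managers were excluded from the study". No comparable exclusion is stated for university 1.

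The same section fixes the arms by employer. After Time 1 recruitment "the intervention training became available for managers at university 1", and "Managers at university 2 (the control group) were offered the intervention at the conclusion of the study". Organizational Settings describes university 1 as a medical university with a cancer focus and university 2 as a unionised public institution. It adds that, at both, "participants completed a baseline survey and two follow-up surveys approximately 3 and 5 months after the baseline survey".

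The Data Analysis section plans mixed models for employees nested in supervisors and employers, and refers to two measurement occasions. It gives these models two aims: to detect pre-post change, and to detect group differences in how supervisors' family-supportive behaviour relates to employee outcomes. Condition A versus Condition B is one of two examples of such groups. It does not say which university is which condition. It writes no difference between conditions in change over time, names no adjustment for employer or manager frame, and states no limit on attributing a difference to the training.

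**The concern.** The only protection that a two-site, non-randomised design has against stable differences between the sites is the baseline survey. The Time 1 data exist at both universities, but the plan as written does not use them to compare change between the arms. A within-arm change mixes the training with whatever else happened over about 5 months. A between-group difference in a behaviour-outcome relationship may have been there before anyone was trained.

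Key Objectives includes an evaluation of the programme's readiness for commercial use, so whether a difference can be attributed to the training matters. Data collection is described as complete, so only the analysis and the wording of the conclusion can still change.

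**Working it through.** **1. Counts.** The one derived figure in the documents is training uptake: 174/368 = 0.473, which reproduces the stated 47%. Invited managers: 368 + 136 = 504. Invited employees: 1,899 + 811 = 2,710. These are invitees, not respondents. Employers per condition: one and one.

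**2. What pre-post change estimates.** Write the mean outcome in arm g (1 = university 1, 2 = university 2) as a_g at Time 1 and a_g + d_g at follow-up, plus a training effect τ at follow-up in arm 1 only. Here a_g is the stable level and d_g the untreated change.
- Pre-post change in arm 1 = τ + d_1. University 2 does not enter.

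**3. What a group difference in relationships estimates.** Let β_g be the stable slope of outcome on supervisor behaviour.
- With no training effect, the difference is β_1 − β_2, which need not be zero. With assumed slopes of 0.2 and 0.3 it is 0.2 − 0.3 = −0.10.
- A gap in level, a_1 − a_2, does not enter this quantity. A stable level gap alone therefore cannot create it.
- Expressed as change from Time 1, the stable slopes cancel: (0.2 − 0.2) − (0.3 − 0.3) = 0.

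**4. What the condition-by-time contrast estimates.**
- [(a_1 + d_1 + τ) − a_1] − [(a_2 + d_2) − a_2] = τ + (d_1 − d_2).
- Stable levels cancel on the scale of the model. The difference in untreated change, d_1 − d_2, remains. It may have either sign, and the documents give nothing from which to size it.

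**5. Employer-level information.** Degrees of freedom for employers within condition = 2 employers − 2 conditions = 0. The model cannot estimate variation between employers, so the standard error of the contrast leaves it out.

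The following illustrates that last point only; every variance input is assumed. Scale the per-employee change to variance 1. Let ρ be the manager intraclass correlation, ρ_E the share of variance from employer-specific change, n the employees and m the employees per manager (1,899/368 = 5.16 and 811/136 = 5.96).
- V = sum over arms of [1 + (m − 1)ρ]/n, and the true error rate of a nominal two-sided 5% test is 2{1 − Φ(1.96·√V/√(V + 2ρ_E))}.
- Full response, ρ = 0.05: V = 1.208/1,899 + 1.248/811 = 0.00218, so √V = 0.0466. With ρ_E = 0.001, √(V + 0.002) = 0.0646, and the error rate is about 16%.
- Ranges over ρ from 0.05 to 0.10 and response from 30% to 100% (m held fixed):

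| Assumed ρ_E | True type I error |
|---|---|
| 0 | 5% |
| 0.001 | 8% to 16% |
| 0.01 | 28% to 54% |
| 0.05 | 58% to 78% |

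**The case against.** The strongest reply is that the plan already contains the ingredients: mixed models, employers as a level, pre-post change and a comparison of conditions. The A-versus-B wording is only an example in a parenthesis, and a competent analyst might well fit condition by time. That the two conditions are the two universities is itself an inference. The frames are openly described, no passage claims randomised allocation or draws a causal conclusion, and limitations are often left to the report.

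Much of this is fair. The plan leaves the contrast unwritten; it does not rule it out. But a plan that leaves the main comparison open does not settle it. The mention of two occasions, against three surveys in Organizational Settings, means that even a sympathetic reader cannot tell which follow-up would be used.

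Some stronger readings are tempting and are not supported:
- **Prior training and academic role differ by arm.** This is plausible, but neither prior training at university 2 nor the academic share at university 1 is given. The contacts' lists carried "role designations (i.e., manager or employee"), but survey contents are not set out, so items on role or training cannot be excluded.
- **The plan compares arms at follow-up only.** It proposes no such comparison.
- **Random selection at university 1 means randomisation.** It describes who was invited, not allocation to arm.

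**Conclusion.** The point holds as a matter of analysis and stated conclusion. Condition, employer and manager sampling frame coincide completely. Read literally, neither planned analysis compares change between the arms: one omits the control group, and the other can be non-zero at baseline.

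The size of any bias is unknown. A reader might infer a bound from assumed differences between academic and other managers. The documents support none, because employer-specific trends also enter and can act in either direction. The slopes of 0.2 and 0.3 and the error rates in the table rest on assumed inputs. They show how the problem works, not how large it is in this trial.

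The condition-by-time contrast is better than what is written, but it removes stable differences only. Even identical manager frames would leave employer confounded with condition. This is a change that should be made, not evidence that any result is wrong.

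**What to change.** In the Data Analysis section:

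1. State which university is Condition A and which is Condition B.
2. Define the training effect as the condition-by-time contrast from Time 1 in the planned mixed model. Name the follow-up used (Time 2, Time 3 or both), and reconcile this with the reference to two occasions.
3. Express any A-versus-B difference in behaviour-outcome relationships as change from Time 1, or label it descriptive.
4. Limit the conclusion to a non-randomised comparison of two employers with different manager frames. State that the contrast removes stable differences only and that differing trends could bias it in either direction by an unknown amount. State also that, with one employer per arm, its standard error and p-value do not reflect employer-level variation. If one employer per arm is already addressed as a limitation elsewhere, place this wording there.

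The cost is one contrast in a model family already planned, using Time 1 data already collected at both universities, and a narrower stated conclusion. No new data are needed.

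### Does the undefined phrase about participating supervisors leave employees open to exclusion when their manager missed a survey?

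*Combined protocol and SAP*

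**What the plan says.** The Data Analysis section of the combined protocol and SAP introduces its mixed models by describing a clustered design with "all participating employees within participating supervisors and employers at two time-points". The models are to detect change from before to after training and differences between groups. The section defines neither a participating supervisor nor an analysis set.

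Organizational Settings defines a manager by role only (someone with direct reports) and gives the survey schedule: "For both universities, participants completed a baseline survey and two follow-up surveys approximately 3 and 5 months after the baseline survey".

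Participants, Recruitment, and Survey Procedures supplies the rest:

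- The university 1 contact "randomly selected 368 managers", whose invited direct reports numbered 1,899. University 2 listed "136 managers and 811 employees".
- Each site's contact named every invitee's "manager to allow for linking in subsequent data analyses".
- On the training at university 1: "These managers were sent five recruitment emails about the training over the course of approximately one month".
- After the webinar, "managers and employees at both universities were invited to participate in Time 2 and Time 3 surveys". No condition on an earlier response is attached.
- "Managers at university 2 (the control group) were offered the intervention at the conclusion of the study".

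**The concern.** Managers and employees were surveyed separately, so an employee can have data when the manager has none. The only sentence that describes the analysis data qualifies supervisors as participating and then counts two occasions where three took place. An analyst who treats that word as a filter has several candidates: any survey, Time 1 plus Time 2, Time 1 plus Time 3, all three surveys, or some training.

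The choice could matter for validity as well as numbers. Time 2 and Time 3 came after university 1 managers had been emailed about the training and invited to the webinar, and university 2 managers had no such contact. Keeping employees only if their manager answered a follow-up would select on something that happened after the intervention began in one group, and the selection need not act equally in the two groups. The section also plans models of supervisors' family-supportive behaviors without saying who rates them, so it is unclear which models need the manager's own survey at all.

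**Working it through.** **Inputs.** From Participants, Recruitment, and Survey Procedures: 368 managers and 1,899 employees invited at university 1; 136 managers and 811 employees at university 2; 174 university 1 managers (47%) who finished one or more training components.

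**The plan's own figure.** 174 / 368 = 0.473, which rounds to the stated 47%. The base for that percentage is every invited manager. No survey response count appears in the text. Figures 1 and 2 are not shown and may hold some, so their absence is not held against the plan.

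**Invited totals.** 368 + 136 = 504 managers; 1,899 + 811 = 2,710 employees.

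**Possible meanings of a participating supervisor.**

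1. *Took some training.* This leaves 0 of 136 university 2 managers during the study, because they were offered the intervention only afterwards. It would remove the control group, so it cannot be meant. At university 1 alone it would drop 368 - 174 = 194 managers. Assuming the average of 1,899 / 368 = 5.16 invited employees per manager applies to them, that is 194 x 1,899 / 368, or about 1,001 of 1,899 employees.
2. *On the site list and invited.* This fits both universities. It also matches usage in the recruitment section, where people who were sent recruitment emails or reminders are called participants. All 504 managers and 2,710 employees stay eligible, and the question of which surveys count does not arise.
3. *Answered surveys.* This also fits both universities, and Organizational Settings uses the word in that sense. How many managers remain depends on response rates that the text does not give. As an illustration only, suppose 60% of managers answer each survey. With independent answers across surveys, any survey keeps (1 - 0.4^3) x 504 = 472 managers, Time 1 plus one named follow-up keeps 0.6^2 x 504 = 181, and all three keeps 0.6^3 x 504 = 109. If the same managers answer every time, each definition keeps 0.6 x 504 = 302. The spread comes from the independence assumption, so it is no evidence of an effect in this study. It also counts managers, whereas the worry is about employees.

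**Is there an exclusion?** The sentence describes the layers of the data and leads straight into the choice of mixed models. It does not say that employees of a non-responding manager are removed. Three other features point towards keeping them: the sentence speaks of all participating employees, the links come from the site lists, and the follow-up invitations carry no condition.

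**Two versus three time-points.** This is a conflict between two current passages, but it concerns the time factor and not who is in the data. Replacing two by three would leave the meaning of the supervisor phrase as it was, and defining the supervisor phrase would not say which follow-up counts as post-training.

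**The case for a change.** The best reply is that this is the only description of the analysis data, so an analyst must either act on the qualifying word or ignore it, and the plan does not say which. Mixed models can use incomplete repeated outcomes, but they do not decide which clusters enter. Writing the rule down would take two or three sentences and no new data.

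Much of this stands. The term is undefined, the count of time-points is wrong against the survey schedule, and selecting on a follow-up response would be a poor choice if anyone made it. What does not stand is the step from an undefined word to a risk in this plan. The harmful reading requires a response condition that no passage states. The reading that fits the linking procedure loses nobody. Where a model does need a variable from the manager's survey, employees whose manager gave none lack that covariate whatever the sentence says. Who rates supervisor behavior is a question about measurement and should be judged as such.

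A rule written now would also do little. The design sections report data collection in the past tense, so it could not count as pre-specified. It would not touch the larger limitation either: each condition is a single university.

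**Conclusion.** No change to the plan follows. The missing definition is a gap that an analyst fills sensibly: an employee with survey data belongs to the manager on the site list and to that manager's university. Nothing in the documents contradicts that, and on that reading all 504 invited managers and 2,710 invited employees remain eligible. No loss of employees and no bias is shown, and neither can be sized from the text.

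The reference to two time-points is best read as a slip in the description of the design, since the same mixed models can take three occasions. It does leave unnamed which follow-up is the post-training measurement. That is a separate matter and does not bear on whether employees are retained.

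This conclusion assumes that the sentence describes nesting, as its wording and position suggest, and that no exclusion based on manager response was applied. A document showing that employees had been dropped because their manager missed a follow-up survey would reopen the point.
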